## 11.1.5. Follow up Phase

At the end of the 6-week period, participants who had quit smoking will be scheduled for a follow-up visit at 4 months (from the screening visit). Those who continue to smoke will complete an "end of study" form and will not be required to return for further followup. The 4 month follow-up visit will include the same assessments and questionnaires as the weekly visits. All attempts will be made to minimize drop-out and ensure that the study subjects present for the 4 month follow-up visit, including periodic study reminders.

All follow-up procedures are shown in the Time and Events Schedule (Attachment 1).

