## 4. OVERALL RATIONALE FOR THE STUDY

In light of the positive results of the safety and efficacy, feasibility trial in Beer Yakov Mental Health Center with the DTMS treatment with the HADD-coil for treatment of smoking cessation (as described in section 2.3), a controlled, randomized, double-blind trial will be carried out, in which the DTMS treatment will be compared to sham treatment. This study is meant to confirm a lack of bias in the results of the pilot study. The Brainsway DTMS device is intended as an aid to smoking cessation. A study design was chosen that would evaluate the safety and effectiveness for this intended use. Treatment will be administered over a 6 week period and follow-up assessments will be conducted at 4 months. The treatment period is sufficient to investigate the effects of the DTMS treatment.

The clinical study design includes multiple measurements of safety and effectiveness parameters. The design is meant to demonstrate that the device shows superiority compared to sham treatment over six treatment weeks, at the 4 months follow up. The study design allows the results to clearly demonstrate that DTMS treatment is superior to sham treatment for the intended treatment paradigm.

The aim of the study is to evaluate the safety and efficacy of DTMS compared to sham treatment as an aid to smoking cessation in chronic ( $\geq 10$  cigarettes/day) cigarette smokers.

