Subjects will be asked to select a target quit date (TQD within 7-14 days of the first treatment session. Participants will be asked to refrain from smoking nicotine for at least two hours prior to the baseline visit and prior to each treatment session. Prior to treatment stimulation onset, a smoking related cue will be presented to the subject. Immediately after the offset of the smoking cue presentation (while memory is reactivated) active or sham DTMS stimulation will be administered. It has recently been demonstrated that in nicotine-deprived smokers, reward and attention circuits are reactivated by mere exposure to smoking-related images, in contrast with neutral images (Due et al., 2002). The preliminary study conducted with the Brainsway DTMS device (described in section 2.3) found that induction of craving by a smoking cue immediately prior to DTMS over the prefrontal and insular cortices induces a stronger effect on nicotine addiction relative to DTMS treatment alone. We propose that presentation of the smoking cue causes the nicotine-related memories and associated craving to become activated and therefore, labile for interference, as previously suggested (Amiaz et al., 2009; Dudai, 2006).

The study design is directed towards a comparison, between active treatment and sham, at 6 weeks and 4 months follow-up.

Efficacy will be assessed using the primary efficacy measure of abstinence, where abstinence is defined as a subject's self-report (in diary) of no smoking (0 cigarettes/day), confirmed by urine cotinine levels  $\leq 200$  ng/ml. Additionally, several subject assessment scales will be used during the course of the study to assess nicotine craving and nicotine withdrawal symptom.

Safety will be assessed, including monitoring of adverse events, vital signs, physical examination and auditory threshold testing. The Mini-Mental State Exam (MMSE) and the Buschke Selective Reminding Test (BSRT) cognitive tests will also be used to assess changes in cognition and memory during the study period.

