## 11.2. Efficacy and Safety Evaluations

All subjects will undergo the following efficacy and safety evaluations at each of the follow-up visits. All efficacy and safety measures and the time table for performing them are shown in the Time and Events Schedule provided in Attachment 1 to the study protocol.

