### 13.2. Study Endpoints

# 13.2.1. Primary Efficacy Endpoint

The primary endpoint is the four-week continuous quit rate (CQR), representing abstinence during a consecutive 4 week period. Weekly abstinence is defined as a subject's self-report (in diary) of no smoking (0 cigarettes/day during the whole week), confirmed by urine cotinine levels  $\leq 200$  ng/ml. A missing confirmatory test will be considered negative, if the previous and the following weekly or 4 month follow-up confirmatory tests are negative. Quit rates are defined as the ratio of the number of patients meeting the quit criterion for at least 4 consecutive weeks to the number of patients initially treated and having at least one post-baseline assessment.

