#### 13.9.5. Efficacy analyses

• The continuous quit rate (CQR) at the 6 weeks visit will be compared between the study arms with a chi-squared test. In addition the CQR will be modeled with logistic regression; baseline daily number of cigarettes smoked, sex and center will be used as covariates.

Prognostic factors and sensitivity analysis for the CQR at the 6 week and/or 4 month follow-up visits will be performed in the following manner: adjustment for other covariates such as demographics or other baseline characteristics (e.g., sex, age, race and history of smoking) may be performed by adding these variables to the above described logistic model.

- Weekly point prevalence abstinence rates will be analyzed in the same manner.
- Daily number of cigarettes smoked will be presented over time and analyzed with a repeated measures analysis of covariance model. Baseline daily number of cigarettes smoked, sex and center will be used as covariates.

The analysis will be presented for all subjects in the analysis set and for the non-quitters only.

 Effect on withdrawal symptoms as measured by weekly scales measuring nicotine craving and dependence/withdrawal, including Fagerstrom Test for Nicotine Dependence (FTND), Minnesota Nicotine Withdrawal Scale SelfReport (MNWS), Tobacco Craving Questionnaire–Short Form (TCQ-SF) and Nicotine Craving Scale.

Fagerstrom Test for Nicotine Dependence scores will be presented in tabular form and compared between the treatment arms with chi-squared tests.

Minnesota Nicotine Withdrawal Scale Self-Report scores, Factor structure of Tobacco Craving Questionnaire–Short Form scores, and Nicotine craving scale scores will be presented over time and analyzed with a repeated measures analysis of covariance model. Baseline daily number of cigarettes smoked, sex and center will be used as covariates.

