### 13.9.6. Safety analyses

Adverse events (AE) will be presented by seriousness, severity and relation to treatment by treatment group. Serious adverse events will be listed and discussed individually. The incidence of potentially clinically significant vital sign measurements (BP, pulse and weight) will be presented at the 6 week and 4 month follow-up visits by treatment group. Descriptive statistics as well as changes from baseline will also be presented by study group at each scheduled visit.

Hearing loss will be presented in a tabular form at the 6 week visit by treatment arm. MMSE and BSRT will be tabulated at the 6 week and 4 month follow-up visits by treatment group.

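### Only week-6 quitters return at 4 months, so between-arm results that need attendance at that visit compare outcome-selected subsets

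*Protocol*

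**What the plan says.** **Who returns.** Section 11.1.5 states that after six weeks "participants who had quit smoking will be scheduled for a follow-up visit at 4 months". Those who continue to smoke complete an end-of-study form and "will not be required to return for further followup". Section 11.2 reads differently: "All subjects will undergo the following efficacy and safety evaluations at each of the follow-up visits". Sections 11.2.3 to 11.2.8, 11.4.1 and 11.4.4 place the craving, dependence and withdrawal scales, MMSE, BSRT, physical examination and vital signs at 4 months without restricting them to quitters.

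**What is to be compared.** Section 6: "The study design is directed towards a comparison, between active treatment and sham, at 6 weeks and 4 months follow-up". Section 4 says the design is meant to show "superiority compared to sham treatment over six treatment weeks, at the 4 months follow up". Section 13.9.6: "MMSE and BSRT will be tabulated at the 6 week and 4 month follow-up visits by treatment group"; vital signs are presented the same way. Section 13.9.5: "Daily number of cigarettes smoked will be presented over time and analyzed with a repeated measures analysis of covariance model", with no last time point named.

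**What protects quit status.** Section 11.3.1 divides by all patients initially treated; sections 13.2.1 and 13.2.3 add the condition of at least one post-baseline assessment. Section 13.9.8 classifies dropouts and subjects lost to follow-up as non-abstinent. The primary chi-squared test in section 13.9.5 is at week 6.

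**The concern.** Attendance at 4 months depends on smoking status at week 6, which is a post-randomisation outcome and the one treatment is expected to change. If treatment works, the active attenders include people who would not have quit on sham, while the sham attenders are a smaller and more strongly selected group. Randomisation no longer makes the two comparable. A difference between arms in 4-month cognition, blood pressure, craving or withdrawal could then reflect who came back, and a true difference could be masked.

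Two things are at stake. The 4-month safety tables would show a minority of those exposed, under a by-treatment-group layout that invites a between-arm reading. And an analyst following sections 4 and 6 literally could report a 4-month treatment comparison that the visit schedule cannot support. A later analysis plan cannot recover data that the schedule does not collect.

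**Working it through.** **Inputs.** Sham quit rate 18% and difference 20 points, hence 38% on active; 82 evaluable per arm; 37% drop-out (section 13.4). Maximum 135 randomised per arm (synopsis).

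**The plan's own figure.** The protocol gives no size for the 4-month comparison. Its evaluable number for week 6 does reproduce:
- Fixed design, unpooled variance, two-sided 5%, 80% power: (1.960 + 0.842)² × (0.18 × 0.82 + 0.38 × 0.62) / 0.20² = 75.2 per arm.
- Two looks with equal bounds at 65% information inflate this by 1.082: 75.2 × 1.082 = 81.4, that is 82 per arm.

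So 18% and 38% are the rates the design rests on.

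**Expected 4-month attenders, if quitting means meeting the CQR criterion (assumption).**
- Active: 135 × 0.38 = 51.3. Sham: 135 × 0.18 = 24.3.
- Without 4-month data: 62% of active, 82% of sham, and overall (270 − 75.6) / 270 = 72%.
- Attenders who are active: 51.3 / 75.6 = 68%, against 50% as randomised.

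**If the 37% drop-outs count as failures.**
- Active: 0.38 × 0.63 = 23.9%, and 135 × 0.239 = 32.3. Sham: 0.18 × 0.63 = 11.3%, and 135 × 0.113 = 15.3.

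**How different the subsets are.** If everyone who quits on sham would also quit on active (assumption), then (0.38 − 0.18) / 0.38 = 53% of active attenders would not have attended under sham.

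**Size of a purely spurious difference.** Take a 4-month measure with no treatment effect and correlation r with a normally distributed propensity to quit (assumption). Select the top 38% in one arm and the top 18% in the other. By simulation, the arm means differ by 0.09 SD at r = 0.2, 0.18 SD at r = 0.4 and 0.27 SD at r = 0.6. The range of r is assumed; the protocol gives no figure.

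**Why the denominator matters for quit status.** Section 13.4 gives pilot quit rates of 44% and 13% at three weeks, and 33% and 9% at six months. Over everyone, the late contrast is 33 − 9 = 24 points. Among early quitters only, assuming late quitters are a subset of early ones, it is 33/44 = 75% against 9/13 = 69%, about 6 points. The same data give very different answers depending on whether released smokers stay in the denominator.

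**The case against.** Several parts of the opposing case stand, and each blocks a stronger reading.

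- **A reader might infer that every 4-month efficacy comparison is between selected subsets.** Not for quit status: sections 11.3.1, 13.2.1 and 13.2.3 keep treated subjects in the denominator, and a week-6 smoker has already broken continuous abstinence. Only someone who quits later would be misclassified. What remains is a gap: section 13.9.8 names dropouts and subjects lost to follow-up, whereas a smoker released on schedule can be a completer under section 12.1.
- **A reader might infer that cigarettes per day, a secondary endpoint in the testing hierarchy, is contaminated.** Section 13.9.5 does not say that 4-month values enter the model, and time points are commonly left to the analysis plan. Release also depends on recorded week-6 smoking, so a likelihood model that uses each subject's own earlier data is not plainly invalid. The remaining worry is extrapolation if late values are included.
- **A reader might infer that the primary endpoint is biased,** because a missing cotinine test may be bridged "if the previous and the following weekly or 4 month follow-up confirmatory tests are negative" and only returning quitters can supply the 4-month test. The preceding test must still be negative and the diary must show no smoking. Subjects released as smokers would be non-abstinent anyway. No bias is shown.
- **The 4-month outputs are not confirmatory.** The safety tables carry no test, the scales are exploratory, and MMSE, BSRT and vital signs are also scheduled at week 6 without selection.

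None of this removes the conflict between sections 11.1.5 and 11.2, or the 4-month between-arm aims in sections 4 and 6.

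**Conclusion.** The point holds for measures that need attendance: vital signs, physical examination, MMSE, BSRT, FTND, MNWS, TCQ-SF, craving and any 4-month cigarette count. These will be seen in about 51 active and 24 sham subjects of 135 per arm, or about 32 and 15 if drop-outs count as failures, and the two groups are not comparable by randomisation.

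The counts rest on the planning rates and on reading quitting in section 11.1.5 as the CQR criterion, which that section does not define. If week-6 abstinence alone qualifies, more would return and the missing share would be below 72%.

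The 4-month quit rate is largely sound and needs one clarification. The primary week-6 comparison is not affected on anything shown here. This should be corrected, but it does not threaten the main result.

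**What to change.** 1. Reconcile sections 11.1.5 and 11.2 on who attends at 4 months, and define what having quit means for that visit.
2. If the visit remains for quitters only, state in sections 13.9.5 and 13.9.8 that 4-month between-arm inference is limited to quit status over the full primary analysis set, with smokers released at week 6 and non-attenders counted as non-abstinent. Align sections 4 and 6 with this.
3. State in section 13.9.5 that the repeated-measures models for cigarettes per day and the scales use data to week 6 only.
4. Label all other 4-month efficacy and safety summaries, including those in section 13.9.6, as descriptive in week-6 quitters, and make the between-arm safety comparison at week 6.

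The cotinine bridging rule should stay as it is: changing it would redefine the primary endpoint without a demonstrated need.

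**Cost.** Wording only, with no extra visits. The 4-month safety and scale data would no longer support a statement about one arm against the other. If such a statement is wanted, all randomised subjects would have to be followed to 4 months, which does mean extra visits.

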## 11.2. Efficacy and Safety Evaluations

All subjects will undergo the following efficacy and safety evaluations at each of the follow-up visits. All efficacy and safety measures and the time table for performing them are shown in the Time and Events Schedule provided in Attachment 1 to the study protocol.

# 11.2.1. Nicotine Use Inventory - Self-report of Number of Cigarettes Smoked

Participants will be asked to keep a record of their smoking behavior on a daily diary card, including the number of cigarettes smoked each day. The information recorded on the diary cards will be reviewed at each visit. The number of cigarettes smoked per day and the length of time since last cigarette will be reported on the daily diary cards. The number of cigarettes smoked recorded on the subjects' diary will be used to assess abstinence.

## 11.2.2. Biochemical Verification - Urine cotinine samples

Quantitative assessment of urine cotinine levels (nicotine metabolite) will be performed. Urine cotinine levels will be measured from a urine sample and sent to a core laboratory for analysis. The cotinine assessment will be performed at Baseline, at the weekly visits during the treatment phase and at the 4 month follow-up visit. The biochemical verification of cigarette smoking will be used to assess abstinence.

## 11.2.3. Nicotine Craving Scale (7 point VAS scale)

A Nicotine Craving Scale, based on a 7 point Visual Analogue Scale (VAS), where 1 is defined as "Very definitely not" and 7 is defined as "Very definitely", and on which the subject will mark his/her subjective craving in response to the question - "How much do you crave a cigarette right now?" will be used. This "desire to smoke" rating has been shown to be sensitive to assess self-reported levels of craving in nicotine smoking (Schuh and Stitzer, 1995; King and Meyer, 2000). The results of the Nicotine Craving Scale will be recorded at Baseline, at each treatment during the 6 weeks of treatment and at the 4 month follow-up visit. The Nicotine Craving Scale will be administered before the smoking cue prior to each treatment, after the smoking cue before each treatment and after each treatment.

# 11.2.4. Fagerstrom Test of Nicotine Dependence (FTND) (Heatherton et al., 1991)

The Fagerstrom Test for Nicotine Dependence (FTND) assesses physical nicotine dependence. The earlier Fagerstrom Tolerance Questionnaire was improved by modification, and a revised scoring for the FTQ, called the Fagerstrom Test for Nicotine Dependence (FTND) was developed. The FTND consists of six of the original items (nicotine rating and inhalation have been eliminated) with revised scoring for two of the items (TTF - Time to the first cigarette of the day, and CPD - Cigarettes per day). The FTND has acceptable levels of internal consistency, and is closely related to biochemical indices of heaviness of smoking. The FTND scores will be assessed at Baseline, at the weekly visits during the treatment phase and at the 4 month follow-up visit.

# 11.2.5. Minnesota Nicotine Withdrawal Scale (MNWS) (Hughes and Hatsukami 1986)

The Minnesota Nicotine Withdrawal Scale (MNWS) is the one most frequently used scales for assessing nicotine withdrawal symptoms. This eight-item scale measures withdrawal symptoms (i.e., craving, irritability, anxiety, difficulty concentrating, restlessness, increased appetite or weight gain, depression, and insomnia) listed in the Diagnostic and Statistical Manual of Mental Disorders (4th ed.; DSM–IV; American Psychiatric Association 1994) and these symptoms are generally scored on an ordinal scale ranging from 0 (not present) to 4 (severe). The MNWS has been validated in multiple studies (Hughes, 1992; Hughes, et al 1991; Hughes et al 1986). In both the Hughes (1992) and Hughes et al. (1991) studies, although observer ratings of MNWS withdrawal symptoms were not highly concordant with self-ratings, both sets of ratings were sensitive to abstinence effects, showing evidence of good reliability and validity for the scale. The MNWS scores will be assessed at Baseline, at the weekly visits during the treatment phase and at the 4 month follow-up visit.

# 11.2.6. Tobacco Craving Questionnaire (TCQ- SF)

The Tobacco Craving Questionnaire (TCQ) is a valid and reliable 47-item self-report instrument that assesses tobacco craving in four dimensions: emotionality, expectancy, compulsivity, and purposefulness. A short, 12-item version of the TCQ was constructed by selecting three items from each of the four factors that exhibited optimal within-factor reliability (Cronbach's alpha coefficient) and inter-item correlation. These items are rated

on a Likert-type scale from 1 (*strongly disagree*) to 7 (*strongly agree*). The TCQ–SF reliably measures the same multidimensional aspects of tobacco craving as the TCQ when tested under different experimental conditions and over repeated assessments (Heishman et al., 2003; Singleton et al., 2003). The use of the TCQ–SF is recommended in clinic and research settings where time may be limited, yet a multidimensional assessment of tobacco craving is desired. The TCQ–SF scores will be assessed at Baseline, at the weekly visits during the treatment phase and at the 4 month follow-up visit.

#### 11.2.7. Mini-Mental State Exam (MMSE)

The mini-mental state examination (MMSE) or Folstein test is a brief 30-point questionnaire test that is used to assess cognition. It is commonly used in medicine to screen for dementia. In the time span of about 10 minutes, it samples various functions, including arithmetic, memory and orientation. The MMSE test includes simple questions and problems in a number of areas: the time and place of the test, repeating lists of words, arithmetic, language use and comprehension, and copying a drawing. Any score over 24 (out of 30) is effectively normal. The normal value is also corrected for degree of schooling and age. It was introduced by Folstein et al in 1975, and is widely used with small modifications. Subjects will be assessed for cognitive changes using the MMSE, at Screening, Baseline, at the 6 week visit and at the 4 month follow-up visit.

11.2.8. Buschke Selective Reminding Test (BSRT)

The Buschke Selective Reminding Test (BSRT) (Buschke, 1973 (40)) is used to provide a traditional measure of verbal learning and memory using 12-word lists, 10 trials, and 2hr delayed free recall, followed by reacquisition of the list (10 trials) (4 alternate forms). Since subjects are only reminded of words not recalled on the previous trial, this task provides more information on encoding and retention than other list learning tasks. This task is especially sensitive to anterograde amnestic effects of ECT and other interventions (41). The primary dependent measure will be total words correctly reported at the second administration (reacquisition). Subjects will be assessed for cognitive changes using the BSRT, at Baseline, at the 6 week visit and at the 4 month follow-up visit.

## 11.3. Efficacy Measures

All subjects will undergo the following efficacy measures.

11.3.1. Abstinence and Continuous Quit Rates (CQR)

Abstinence is defined as a subject's self-report (section 11.3.1) of no smoking (0

cigarettes/day), confirmed by urine cotinine levels  $\leq$ 200ng/ml (section 11.3.2). The "cutoff" value of urine cotinine) is recognized as 200 ppm or 200ng/ml) for the determination of abstinence. Subjects with cotinine levels above this value will be considered to have not stopped smoking. Continuous Quit Rates (CQR) is defined as the ratio of the number of patients meeting the quit criterion (i.e., abstinence during a consecutive 4 week period) to the number of patients initially treated, will be assessed at Baseline, at the weekly visits during the treatment phase and at the 4 month follow-up visit.

